4. SPECIFIC AIMS/HYPOTHESES

Our primary objective is to assess stone dusting ablation efficiency (Joules/stone volume ablated) between both laser systems *in vivo* for ureteroscopic stone treatment (Ventimiglia et al., 2021, 2023; Corrales and Traxer, 2022). Secondary objectives include assessing stone dusting ablation speed (stone volume ablated/lasing time), stone-related clinical outcomes, effect of hard stones (>1000HU) on ablation efficiency, and safety/complication profile of both laser systems.

We hypothesize that dusting ablation efficiency and speed of the p-Tm:YAG laser will be non-inferior to TFL for the treatment of renal stones totaling 7-20 mm in diameter with similar clinical and safety/complication outcomes.

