5. BACKGROUND AND SIGNIFICANCE

Ureteroscopic stone treatment is a minimally invasive procedure commonly performed for kidney stones. Recently, the thulium fiber laser (TFL) has demonstrated effectiveness in this procedure. A new laser system developed by Dornier, the Thulio pulsed Thulium:YAG (p-Tm:YAG) is beginning to be studied *in vitro* (Huusmann et al., 2021; Petzold et al., 2021a, 2021b, 2021c, 2021d; Kraft et al., 2022a, 2022c; Kwok et al., 2023) and *in vivo* (Panthier et al., 2023). Dornier Thulio p-Tm:YAG may represent an attractive new laser platform, with comparable properties to TFL including decreased retropulsion, (Petzold et al., 2021b) smaller dust, (Petzold et al., 2021a) and improved ablation efficiency relative to Ho:YAG. (Petzold et al., 2021a; Kraft et al., 2022a; Solano et al., 2023) Moreover, the p-Tm:YAG laser has been shown to be effective in treating a wide range of human stone types. (Kwok et al., 2023). The Dornier Thulio p-Tm:YAG laser has been tested clinically in a limited fashion via pilot studies in URS (Panthier et al., 2023) and the RevoLix Hybrid Thulium Laset (HTL) was studied in mini-PCNL (Bergmann et al., 2023). However, limited research has directly compared its efficacy and safety and no prospective comparative trials have been published. This study aims to investigate whether Dornier Thulio p-Tm:YAG laser is non-inferior to TFL in terms of dusting ablation efficiency (J/mm³) and dusting ablation speed (mm³/s) for ureteroscopic stone treatment.

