Perioperative fields will include total operative time, presence of preoperative alpha blockers, procedure time, laser time, setting of lithotripsy that was used most frequently during the case, total laser energy used, use of active fragment extraction (# of fragments beyond that for analysis/culture), 1st assist skill level (PGY level), use and size of ureteral access sheath, intra-operative complications, and treatment on any anticoagulation.

Postoperative fields will include length of hospitalization, postoperative complications, stone composition, need for ancillary procedures, stent duration, and stone-free status on postoperative low-dose CT imaging (axial slices 2.5mm and sagittal/coronal 3mm) using residual stone ABC grading (0 fragments, <2mm fragments, 2-4mm fragments) as recently recommended by Journal of Endourology. (Stern et al., 2023).

The trial will be a prospective, study of patients with renal stones 7-20 mm in size located at or above the level of the ureteropelvic junction. Total enrollment will be limited to 100 patients (50 ureteral and 50 renal) for the study with goal of 50 patients (25 ureteral and 25 renal) in each arm. This goal recruitment number is based on a power analysis for a noninferiority study utilizing a pre-determined non-inferiority margin of 20%, and was calculated to provide 90% power with a one-sided significance level of 0.025.

Table 1, adapted from (Solano et al., 2023), was constructed using results from recently published studies reporting ablation efficiency (J/mm³). The median ablation efficiency for TFL in the table was of 5.6 J/mm³ (Enikeev et al., 2021) with IQR 3-9.9. Assuming a normal distribution, the median and IQR values were used to estimate mean of 6.2 J/mm³ and standard deviation of 5.2 J/mm³. (Wan et al., 2014; Luo et al., 2018) Non-inferiority margin was set at 20% (6.2-1.2=5.0 J/mm³). Estimated mean difference between TFL and Tm:YAG ablation efficiencies was 0 based on a recent systematic review by an international expert in the field (Solano et al., 2023). Data was input into a validated sample size calculator <https://app.sampsize.org.uk/> as previously described. (Flight and Julious, 2016; Negida, 2020) A sample size of 24 participants per group (n=48 total) was found to provide 90% power to detect a non-inferiority margin of 20% with a one-sided significance level of 0.025.

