| | (Azilgareeva et al., 2022) | 25 | 508.9 (293.2-628.3) | 1124.0 ± 329.0 | 15.0 (11.2-18.3) | 0.6 (0.5-0.9) | 30.8 (22.8-41.2) |

The electronic data will be stored in the REDCap (Research Electronic Data Capture) application (16,17). REDCap is a stand-alone system with no interaction or connectivity to other systems, and the database is located behind the UCSD firewall. Users must have a UCSD provided ID/password to connect to REDCap and their ID must be specifically

authorized in order to access an individual study's data. All changes to the data, and each "record viewed" is logged back to the individual ID with a timestamp. When the case report forms are configured, each field has an attribute that can be set to flag it as an "identifier". This "identifier" is used by REDCap to control certain actions related to the field. REDCap also has several built-in functions to control the exporting of identifying information. Individual users are each granted specific export rights, including – None, De-Identified, and Full. Additional export de-identification options include removing identifiers and dates, hashing IDs and date shifting.

Demographic data, pre-operative, and post-operative data will be summarized using mean, median and quartiles (continuous variables) and frequency and percent (categorical variable).

Intention-to-treat analysis will be performed. Non-inferiority analysis will be conducted for the primary endpoints, with a pre-specified non-inferiority margin of 20%.

Secondary endpoints will be compared using appropriate statistical tests (e.g., t-test, chi-square test). All analyses will be performed using a statistical software package (e.g., SPSS).

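### Ablation speed carries a non-inferiority hypothesis, but the protocol is inconsistent about its rank and its analysis

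*Protocol*

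**What the plan says.** Three parts of the protocol bear on ablation speed.

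- **Hypothesis and aim.** Section 4 reads "We hypothesize that dusting ablation efficiency and speed of the p-Tm:YAG laser will be non-inferior to TFL". Section 5 repeats the aim for both measures, asking whether the new laser is "non-inferior to TFL in terms of dusting ablation efficiency (J/mm³) and dusting ablation speed (mm³/s".
- **Rank.** Section 4 names one primary measure: "Our primary objective is to assess stone dusting ablation efficiency (Joules/stone volume ablated". Speed comes first in the next list: "Secondary objectives include assessing stone dusting ablation speed (stone volume ablated/lasing time".
- **Analysis.** Section 6 states "Non-inferiority analysis will be conducted for the primary endpoints, with a pre-specified non-inferiority margin of 20"%. The paragraph after it states "Secondary endpoints will be compared using appropriate statistical tests (e.g., t-test, chi-square test".

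The sample-size text in section 6 works from ablation efficiency and, separately, from ablated weight in vitro. It has no calculation for speed.

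**The concern.** A non-inferiority hypothesis needs a margin and a confidence limit compared with it. A test of no difference has neither, and a non-significant result from it is compatible with a laser that is slower by more than the margin. The protocol gives speed the hypothesis, but the literal text places it with endpoints that get difference tests.

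The plural in "Non-inferiority analysis will be conducted for the primary endpoints" leaves room for another reading, in which speed is a second primary endpoint. That conflicts with section 4 and leaves speed without sizing. At stake is whether one of the two hypothesised results can be answered. The analysis of efficiency is not affected.

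**Working it through.** **1. The two readings side by side.**

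| | Speed is secondary (section 4) | Speed is primary (plural in section 6) |
|---|---|---|
| Analysis | difference-type tests, given as examples | non-inferiority, 20% margin |
| Answers the hypothesis? | no | yes |
| Sample-size calculation | none | none, although primary |
| Conflict | with the hypothesis and aim in sections 4 and 5 | with the ranking in section 4 |

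Each reading contradicts some part of the text.

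**2. The protocol's own figure.** There is none for speed. The stated 24 per group is for efficiency (margin 1.2, SD 5.2, true difference 0, one-sided 0.025, 90% power). It does not reproduce: 2 × (1.960 + 1.282)² × 5.2² / 1.2² gives 395 per group. That is a separate matter on which this point does not depend. It matters here only for the cost of a fixed testing order. At 50 per arm, efficiency has 1.2 / (5.2 × √(2/50)) = 1.154, so power is Φ(1.154 − 1.960), about 21%.

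**3. Inputs for speed.** These are TFL rows of Table 1 in section 6, with 50 per arm as the enrolment goal, so √(2/50) = 0.2. For medians with quartiles I used the conversions that the protocol cites: mean = w(q1 + q3)/2 + (1 − w) × median, with w = 0.7 + 0.39/N, and SD = (q3 − q1) / (2z), with z the normal quantile at (0.75N − 0.125)/(N + 0.25). As a check, the efficiency row 5.6 (3-9.9) with N = 149 gives mean 6.20 and SD 5.17, which match the protocol's 6.2 and 5.2.

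For the sizing series, 2.33 (1.33-4.65), w = 0.7026. The mean is 0.7026 × 2.99 + 0.2974 × 2.33 = 2.79, and the SD is 3.32 / 1.336 = 2.49.

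**4. Chance that a two-sided 5% t-test is non-significant when p-Tm:YAG is truly 20% slower.** The noncentrality is 0.2 × mean / (SD × 0.2) = mean / SD, with 98 degrees of freedom.

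| TFL row (mm³/s) | Mean | SD | Mean / SD | Power | Non-significant |
|---|---|---|---|---|---|
| 0.86 ± 0.31 (N = 126) | 0.86 | 0.31 | 2.77 | 78% | 22% |
| 8.05 (4.55-11.53) (N = 56) | 8.04 | 5.31 | 1.51 | 32% | 68% |
| 1.7 (1.0-2.8) (N = 153) | 1.84 | 1.35 | 1.37 | 27% | 73% |
| 2.33 (1.33-4.65) (N = 149) | 2.79 | 2.49 | 1.12 | 20% | 80% |

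On the log scale the sizing series has SD ln(4.65/1.33)/1.349 = 0.928 and noncentrality 0.223 / (0.928 × 0.2) = 1.20, so power is 22% and non-significance 78%. The least variable series, taken as log-normal, has log SD √ln(1 + (0.31/0.86)²) = 0.35 and noncentrality 0.223 / (0.35 × 0.2) = 3.19, so non-significance is about 12%.

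A one-sided 0.025 non-inferiority test makes a false claim in 2.5% of trials at a true deficit equal to the margin, by construction.

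**5. A larger deficit.** At 40% slower the noncentrality doubles. On the sizing series it is 2.25, and about 40% of trials are non-significant. On the 0.86 ± 0.31 series it is 5.55, and under 0.1% are.

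**6. Power of a non-inferiority test on speed if the lasers are equal.** The distance to a 20% margin is the same as in step 4, so the power is too: about 22% on the sizing series for a ratio limit of 0.80 on the log scale (20% on the original scale), and 78% on the original scale for the least variable series.

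**The case against.** The best defence is that the text can be read without a wrong test. Efficiency and speed are the only measures hypothesised to be non-inferior, so the plural may simply mean both, and speed would then already have a non-inferiority analysis at 20%. This reading is possible, and for that reason the point is an inconsistency and not a wrong test stated as fact. It does not remove the problem: section 4 names one primary measure, and speed would be a primary endpoint without sizing.

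It is also fair that the t-test is only an example, that no sentence assigns it to speed, and that a t-statistic against a shifted null can test non-inferiority. But section 6 attaches the margin to the primary endpoints alone, so a secondary speed endpoint has nothing to shift to. The exact method could be left to an analysis plan. The hypothesis, the rank and the split of analyses are fixed in the protocol, and these are what conflict.

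Three stronger readings are tempting and are not supported:

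- *A non-significant result will be read as non-inferiority.* No passage states such a rule.
- *A clearly slower laser would probably go undetected.* This depends on the row. At a 40% deficit a non-significant result is not the likelier outcome with 50 per arm, even on the sizing series. That series is also, by its title, one of ureteral stones, whereas the inclusion criteria call for renal stones.
- *An order of testing is missing.* If both measures must succeed, neither an order nor a split of alpha is needed.

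**Conclusion.** The inconsistency stands and should be corrected. Depending on the reading, speed has either an analysis that cannot answer its hypothesis or an undeclared primary status without sizing.

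With 50 per arm and a true 20% deficit, a difference test would be non-significant in about 22% to 80% of trials across the four rows used. This assumes the original scale, approximate normality, equal SDs in the arms and 50 analysed per arm. The log scale lowers the bottom of the range to about 12%. Every value is well above 2.5%. The 20% margin for speed is itself an assumption, since the protocol clearly fixes one only for the primary endpoints.

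The importance is moderate: it affects what the trial may conclude about speed, which section 4 calls secondary.

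**What to change.** Name efficiency the single primary endpoint and put the phrase in section 6 into the singular. Then choose one of two options before any outcome data are reviewed.

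- **(a) Keep the claim.** Make speed the key secondary endpoint, tested for non-inferiority only if efficiency succeeds. Require the lower limit of the two-sided 95% confidence interval (one-sided 97.5%) for the speed ratio p-Tm:YAG/TFL to exceed 0.80. Higher speed is better, and 0.80 carries over the 20% margin, which the protocol should state and justify for speed.
- **(b) Drop the claim.** Remove non-inferiority for speed from sections 4 and 5, and report the difference or ratio with its 95% confidence interval.

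Both are changes of wording, and the fixed order in (a) costs no alpha. The cost of (a) is power: about 22% at 50 per arm on the sizing series if the lasers are equal. The chance of a speed claim also cannot exceed the chance that efficiency succeeds, about 21% on the protocol's own mean, SD and margin. The protocol should say so if it takes (a). Option (b) gives up one hypothesised conclusion but promises nothing that the sample may be unable to deliver.

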7. RESEARCH PARTICIPANTS

We plan to enroll 100 participants in this study at the University of California, San Diego.

Inclusion criteria:

- Solitary renal stone 7 to 20 mm in size or in the case of multiple stones the conglomerate diameter (additive maximal diameter of all stones on axial imaging of computed tomography) of 7-20 mm is required
- Must be a suitable operative candidate for flexible ureteroscopy per American Urological Association guidelines
- Must be 18 years or older
- Must be able to give consent
- Bilateral ureteroscopy will be permitted but only the first side (per surgeon discretion) will be included in the study
- Surgeons participating in the study must be urological attending surgeons or fellows with subspecialty training in Endourology

Exclusion criteria:

- Concomitant stones in the ureter
- Prior ipsilateral upper urinary tract reconstructive procedures or history of ipsilateral ureteral stricture
- Prior radiotherapy to the abdomen or pelvis
- Neurogenic bladder or spinal cord injury
- Pregnancy
- Untreated UTI

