Laser settings will be adjusted at the surgeons' discretion but begin at 0.3 J and 10 Hz (long pulse mode for Thulio and short pulse for TFL). (Petzold et al., 2021a) At the surgeon discretion the joules and/or frequencies can be increased by smallest increments available. If possible, a stone fragment will be removed and sent for stone analysis. An additional fragment may be sent for culture at the discretion of the surgeon. Adequacy of dusting will be defined as stone fragments smaller than the laser fiber diameter. A ureteral stent will be placed at the conclusion of the surgery. A string will be left on the stent at the discretion of the surgeon. Post-operative medical therapy will be an alpha receptor blocker to induce ureteral relaxation if not contraindicated for allergy, cataracts, or history of adverse reaction. Additionally, standard postoperative pain medications will be prescribed at the discretion of the treating surgeon.

The stent will be maintained for 2 to 21 days after surgery. Low-dose CT abdomen/pelvis will be performed at 6 weeks postoperatively to assess for stone-free rate, development or persistence of hydronephrosis/obstruction, and need for ancillary procedures. Telephone calls at 2, 4, and 6 weeks will be placed by the CRC to determine any unreported AEs. First clinic follow-up after stent removal will be performed at 8 weeks after stent removal. Telephone call at 2, 4 and 6 weeks will be made by CRC to determine any unreported AE's.

Lasing time (s), laser energy expended (J), and estimated % of the case completed with dusting will be recorded at the conclusion of the case from the laser data log.

All study procedures are standard of care except for the randomization aspect, which will randomly assign a patient to one of two laser groups, and data collection.

Demographic fields that will be obtained preoperatively include age, gender, ASA (American Society of Anesthesiologists) score (for comorbidity assessment), height, weight, body mass index (BMI), and primary or recurrent stone, prior stone composition(s). Disease fields that will be obtained include stone volume (calculated with maximal axial and coronal dimensions), average stone Hounsfield units, degree of hydronephrosis (mild/moderate/severe), and prior ureteral stenting or nephrostomy tube placement.

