8. RECRUITMENT

Ureteroscopic treatment of renal calculi is the standard of care treatment approach, and thus no treatments will be performed that are not considered standard of care.

Patients will be identified based on operating room schedule, clinic visits or hospital admission. They will be approached in person by study personnel.

Using block randomization, participants will be randomized in a 1:1 ratio to receive either p-Tm:YAG or TFL treatment. Surgeons will be blinded to the assigned laser treatment until in the operating room.

Project subjects will be chosen from the pool of patients presenting in a UCSD Urology clinic with kidney stone disease who have chosen to undergo flexible ureteroscopy with holmium laser lithotripsy. Females of childbearing age are given a pregnancy test prior to the procedure. No person shall be excluded from being offered the trial except those based on the above inclusion/exclusion criteria. Vulnerable groups such as pregnant women, fetuses; neonates; prisoners; children; groups with known cognitive impairment; or institutionalized individuals will not be involved in this project. This project has neither direct benefit to individual participants nor monetary compensation, and as such is less likely to lead to coercion of patient populations.

This project will be requesting a partial waiver of HIPAA authorization to be granted. Identifiers will be protected from improper use by having access restricted to project personnel which is limited to the PI and project coordinator. Identifiers will be destroyed 4 years after the project initiation or 2 years after data collection is complete. Project recruitment could not be possible without access to medical chart information which includes PHI. This access to PHI poses minimal risk as it is not used for reasons other than identifying potential participants. No PHI will be used as part of data collection for the project except name on the Informed Consent Form.

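### In bilateral cases the study side can be chosen after the arm is known, and neither the 7–20 mm rule nor the laser log reading is limited to that side

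*Protocol*

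**What the plan says.** Four statements in the protocol bear on bilateral cases.

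- **Study side.** Section 7, inclusion criteria: "Bilateral ureteroscopy will be permitted but only the first side (per surgeon discretion) will be included in the study".
- **Allocation and blinding.** Section 8: "participants will be randomized in a 1:1 ratio to receive either p-Tm:YAG or TFL treatment", and "Surgeons will be blinded to the assigned laser treatment until in the operating room". The patient is randomised, not the kidney.
- **Size eligibility.** Section 7, for multiple stones: "the conglomerate diameter (additive maximal diameter of all stones on axial imaging of computed tomography) of 7-20 mm is required". No side is named.
- **Laser data.** Section 6 states that lasing time, energy and the estimated share of dusting "will be recorded at the conclusion of the case from the laser data log". The perioperative fields in the same section include "total laser energy used, use of active fragment extraction", again without a side.

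The primary objective in Section 4 is "stone dusting ablation efficiency (Joules/stone volume ablated) between both laser systems". Ablation speed (volume over lasing time) is assessed alongside it.

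**The concern.** Two separate problems arise in a patient who has both kidneys treated.

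**Choice of the measured stone.** Whichever side the surgeon takes first becomes the study side. If that decision falls after the arm is revealed, the stone is selected after randomisation, on the primary endpoint, by someone who knows the treatment. The surgeon also has relevant information. Section 6 collects stone volume and average Hounsfield units before surgery, and Section 4 treats hardness above 1000 HU as a possible influence on ablation efficiency. No intent is needed for such a choice to differ between arms, and no analysis can undo it if the choice was not recorded beforehand.

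**Mismatch of unit.** The endpoint belongs to one kidney, but the eligibility sum and the laser log reading are not confined to that kidney. At stake are whether the study kidney lies in the 7–20 mm range that the hypothesis concerns, and whether the numerator and denominator of J/mm³ (and of mm³/s) describe the same stone.

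**Working it through.** **1. Timing.** The study side is settled by operative order, at the surgeon's discretion (Section 7). The surgeon learns the arm in the operating room (Section 8). No section requires the side to be named or recorded before then. A choice made with knowledge of the arm is therefore permitted. The documents give nothing from which to estimate how often it would happen, or the direction or size of its effect.

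**2. Size rule, read literally (sum over both kidneys).**
- 4 mm on each side: 4 + 4 = 8 mm. Admitted, although the study kidney holds 4 mm.
- 12 mm on each side: 12 + 12 = 24 mm. Refused, although either kidney alone meets 7–20 mm.

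**3. Log reading, read literally (one end-of-case total).** Inputs from Section 6: mean 6.2 J/mm³, SD 5.2 J/mm³, margin 20%, 50 patients per arm. The margin reproduces: 0.20 × 6.2 = 1.24, which the protocol rounds to 1.2. The stated sample size is not used here and does not change with this point.

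Assumptions, because the documents are silent: a bilateral share b of 5–20%, and second-side energy equal to r = 0.5–1 times first-side energy. The total is divided by first-side volume.

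*One bilateral patient, r = 1:* J/mm³ goes from 6.2 to 12.4. If lasing time doubles too, mm³/s halves.

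*Inflation of an arm mean = b × r × 6.2:*

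| b | r = 0.5 | r = 1 |
|---|---|---|
| 5% | 0.16 | 0.31 |
| 10% | 0.31 | 0.62 |
| 20% | 0.62 | 1.24 |

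With the same share in both arms, both means rise by this amount and the expected difference is unchanged.

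*Shift in the arm difference from k more bilateral cases in one arm, r = 1: k × 6.2 / 50.*
- k = 1: 0.12 J/mm³ (0.124 / 1.2 = 10% of the margin)
- k = 3: 0.37 (31%)
- k = 5: 0.62 (52%)

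*What chance produces.* If the decision to treat both sides does not depend on the arm, the imbalance follows a hypergeometric distribution with 50 per arm. The expected absolute imbalance is 2.3 for 10 bilateral patients and 3.1 for 20. The corresponding shifts are 2.3 × 0.124 = 0.29 and 3.1 × 0.124 = 0.39 J/mm³ (rounded), equally likely in either direction.

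*For scale.* The standard error of the difference with the protocol's SD is 5.2 × √(2/50) = 1.04 J/mm³. With b = 10% and r = 1, the mixture has mean 6.82 and variance (5.2² + 6.2²) × (0.9 + 0.1 × 4) − 6.82² = 85.1 − 46.5 = 38.6. The SD is then 6.2 and the standard error 6.2 × 0.2 = 1.24. On the same formula the SD is 5.7 at b = 5% and 7.0 at b = 20%.

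**The case against.** The strongest reply is that the protocol already says only the first side is included. On that view second-side data are excluded, all stones means the stones of the included side, and Section 6 merely does not repeat the restriction for each field. The discretion might also be exercised before the operating room.

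Part of this stands. A reader might infer that the protocol counts both kidneys for eligibility, laser totals and complications. It does not say so; it fails to limit the size rule and the log reading to one side. Nor does it say that surgeons choose the side unblinded, only that nothing prevents it. The 4 + 4 and 12 + 12 mm examples show an ambiguous rule, not an established error. The reply does not remove the problem, though. A single reading at the end of the case cannot supply first-side energy once a second side has been lased, unless someone reads or resets the log in between, and the protocol does not ask for that.

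A reader might also infer that the second side could be treated with the other laser, so that its complications count against the wrong arm. The documents do not support this. Sections 6 and 8 assign the patient, not the kidney, to one laser. The outcome list ("Postoperative fields will include length of hospitalization, postoperative complications, stone composition, need for ancillary procedures") is silent on side, but length of stay and systemic events cannot be divided by side in any case.

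Finally, the shifts as a share of the margin could be taken for bias toward one arm. Under chance allocation their expected value is zero, and the typical shift of 0.29–0.39 J/mm³ is less than half a standard error (1.04).

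**Conclusion.** The concern holds in two limited parts. First, the protocol lets the study side be chosen after the arm is known. This is a real opening for selection on the primary endpoint, of unknown size and direction. Second, the size rule and the log reading are not tied to the study side. Taken literally, this admits study kidneys outside 7–20 mm and mixes two-kidney energy or lasing time with one-kidney volume.

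The second part costs about 0.12 J/mm³ in the arm difference per extra bilateral case in an arm of 50, about 10% of the 1.2 margin. It also raises both means by 0.16–1.24 J/mm³ over the assumed range and widens the spread. It is mainly noise and inflation, not directional bias. These figures rest on an assumed bilateral share of 5–20%, on second-side energy of 50–100% of the first (100% for the per-case shift), and on the decision to treat both sides being independent of the arm. If bilateral cases are rare, the effect is small. The change is worth making because it is nearly free and analysis cannot supply it later.

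**What to change.** 1. Record the study side before randomisation, or at least before the arm is revealed, by a rule that leaves no choice. For example: the kidney that alone meets 7–20 mm or, if both do, the one with the larger stone burden.
2. State that the 7–20 mm conglomerate limit applies to the stones of that kidney.
3. In bilateral cases, record laser energy, lasing time and percentage dusting separately for the study side, by reading or resetting the log between sides.
4. Leave operative order to the surgeon, and reconcile the first-side wording in Section 7 with the pre-named study side, since the named side need not be the one treated first.

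The cost is protocol wording, one extra field, and one extra log reading in bilateral cases. The surgeon no longer chooses which side counts for the study. The sample size and the choice of kidneys to treat are unaffected.
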